Methods: Participants who meet the inclusion criteria will be randomly assigned to the TEHE only or Acupressure only or combined acupressure and TEHE (TEHE plus) or combined MBI and TEHE or control (usual care) group. All exercise groups will be offered a 12-week exercise program. They will be instructed to exercise at home to achieve weekly activity/step goals. Activity/steps and symptoms will be monitored daily using the FitBit and a smart phone application. Weekly summary report of physical activity and symptoms will be sent to participants through a web-based mobile phone application. In addition to the TEHE, the TEHEplus group will receive instructions on how to locate and apply the pressure on the acupressure points and weekly recommendation for acupressure points. The acupressure only group will receive only instruction on how to apply the pressure on the acupressure points through the online training or in person training with weekly recommendation for acupressure points. The MBI+TEHE group will receive a weekly recommendation to add mindfulness based intervention including body scan mindful breathing, and mindful movement. The control (usual care) group will report their symptoms level and monitor physical activity through Fitbit and smartphone application daily. At the end of week 12, in addition to the questionnaires, participants will answer open-ended questions about their opinions on the program. Symptoms will be assessed and blood will be drawn before and after the program. Participants who enrolled in the sub-study will be scheduled for one visit for an MRS.

2. Objectives (include all primary and secondary objectives)

Purpose/Specific Aims:

The study primary aims are to (1) test the feasibility of a 12-week technology-enhanced home exercise (TEHE) program and combined technology-enhanced home exercise and Acupressure (TEHEplus) program among cancer survivors; (2) to determine the effect of the TEHE plus program on fatigue, physical activity and serum biomarkers (Heat Shock Protein 90 and Brain-Derived Neurotrophic Factor) compared to the control (usual care) group.

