Exercise study: In the eligibility screening process, potential participants will be approached and screened by phone for the average fatigue level within the past 7 days at the level of 3 or more on the 0 (no fatigue) to 10 (worse fatigue) Likert scale, the self-report perceived ability to walk for six-minute and the exertion level after the walk on a 0-10 numeric perceived exertion scale (0 = no exertion at all to 10 = maximal exertion). Eligible participants will be asked if they would like to participate and to sign the electronic informed consent.

Sub-study (MRS imaging): Participants who are eligible for the exercise study will be asked to answer additional screening questions by phone to assess the eligibility for the study including

1. In the last five years, have you been diagnosed as having a substance abuse disorder?
2. Do you currently drink alcohol? If yes, how many drinks per day on average? (ineligible if answer 5 or more drinks per day for male and 4 or more drinks per day for female).
3. Do you have
 - a. Implanted cardiac pacemakers, metal aneurysm clips;
 - b. Broken bones repaired with metal pins, screws, rods, plates;
 - c. Prosthetic eye implants,
 - d. Transdermal medications or infusion pumps;
 - e. Bullet fragments or other metal pieces in the body from old wounds;
 - f. Significant work exposure to metal particles;
 - g. Clinically relevant claustrophobia;
 - h. Unable to lie comfortably on the back for up to 4 hours;
 - i. Being pregnant or lactating

Only the participants who eligible for the MRS (answer “No” to the above questions), will be invited to participate in the sub-study.

Recruitment for the MRS imaging

Those participants who consent to participate in the exercise study and eligible for the sub-study will have the option to enroll in the sub-study (MRS). Declining to participate in the sub-study will not affect their participation in the main study. This will be a convenience

Date: September 26, 2024

Principal Investigator: [name]

Application Number: IRB00154198

sampling. Once the participant reviews and sign the sub-study section in the consent form. A study visit for the MRS will be scheduled before the first exercise intervention.

Data collection schedule and procedures:

Exercise study:

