Once the informed consent is signed, instruction video on how to install a smartphone application and activity tracker (Fitbit), study materials will be sent to the participant. The participants will be meet with a research team member online using the participant's preferred method (e.g., FaceTime, Zoom, etc.) to review the equipment instruction, and measure cognitive function and perceived short physical performance online. If travel is feasible, participants will be meet with the research team member in person at the East Baltimore (Wald) Community Nursing Center and Outreach or Sidney Kimmel Comprehensive Cancer Center to set up the study device and measure muscle strength, physical performance and heart rate variability (table 1). Participants will be asked complete the questionnaire package through Redcap survey. The physical activity tracker (Fitbit) and the mEMA application will be installed on the participants' smartphone with written instructions on how to use both devices. Participants will be asked to wear the Fitbit on the non-dominant arm and respond to the mEMA daily for 12 weeks.

Peripheral blood will be drawn at week 1 and week 12 for participants who can complete the study visit in person by a registered nurse or trained research staff at the East Baltimore (Wald) Community Nursing Center and Outreach or at the phlebotomy (research clinical blood draw) at Sidney Kimmel Comprehensive Cancer Center, Johns Hopkins University. The collection of blood samples by venipuncture in this study will include the amount of 15 mL, one time per study visit, 2 visits in 12 weeks. (Confirmation that the blood collection by venipuncture from study subjects, the amounts were drawn will be less than 550 ml in 8 weeks and collection occur less than 2 times per week). Blood will be transferred and processed at the Johns Hopkins School of Nursing biophysiological laboratory.

Sub-study (MRS imaging):

Participants enrolled in the sub-study will be scheduled for the MRS at the National Institute on Aging (NIA) located at Medstar Harbor Hospital. The MRS will be done by the NIA staff. The research assistant will accompany the participants and a registered nurse will be available for consultation throughout the MRS process. Only de-identified data will be shared with the Medstar for data analysis.

Table 1: Data collection process

Tasks	Study visit 1	Weeks											Study visit 2	
		Baseline	1	2	3	4	5	6	7	8	9	10	11	

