The feasibility of the TEHE plus program includes the evaluation of the recruitment and retention, acceptability, compliance, and delivery of the intervention. This study aims to measure the feasibility of the TEHE groups (including all three intervention arms). In the data collection process, the eligible participants recruited patients, a number of participants completing the intervention program will be recorded. Compliance with the intervention will be assessed using data collected from the activity tracker on minutes of moderate-intensity or greater activity. At the end of the program (12 weeks), participants will be asked to complete open questions on their satisfaction and opinion on the intervention and delivery method.

Primary and secondary objectives

The study primary aims are to (1) test the feasibility of a 12-week technology-enhanced home exercise (TEHE) program and combined technology-enhanced home exercise and Acupressure (TEHE plus) program among cancer survivors; (2) the effect of the TEHE program and TEHE plus on fatigue, physical activity and serum biomarkers (Heat Shock Protein 90 and Brain-Derived Neurotrophic Factor) compare to the control (usual care) group.

The secondary aims are (3) compare the effect of the TEHE only, Acupressure only, TEHEplus, and combined TEHE and MBI on fatigue and physical activity; and (4) determine the change in serum biomarkers at week 12 compared to baseline in the TEHE only, Acupressure only, TEHEplus, MBI+TEHE, and control (usual care) groups

Analysis plan

Exercise study:

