The mean and standard deviation of each outcome measure, recruitment rate, drop out, acceptability, tolerability will be calculated per group per study visit. The study primary aim the feasibility of a 12-week technology-enhanced home exercise (TEHE) program and TEHE plus program (***Aim 1***) will be analyzed using descriptive statistics of eligible participants and recruited participants, a number of participants completing the intervention program, compliance (number of participants complete the daily step goal), and participants' satisfaction and opinion of the intervention. To examine the effect of the TEHE program on fatigue, physical activity and serum biomarkers (Heat Shock Protein 90 and Brain-Derived Neurotrophic Factor) (***Aim 2***), the paired t-test will be used to analyze the effect of the program on fatigue, PA and biomarkers at the end of the program compared to baseline. The student t-test will be used to compare the variables among participants in the TEHE program, Acupressure only, TEHEplus, and TEHE +MBI compare to the usual care (control) group.

The secondary aims: The change of fatigue and physical activity level in week 12 compared to baseline will be calculated. Analysis of Variance (ANOVA) will be used to compare the effect of the TEHEplus, combined TEHE, and MBI with the TEHE only and Acupressure only on fatigue and physical activity (***Aim 3***). Change from baseline to 12 weeks will be computed for serum HSP90AA1 and BDNF levels. ANOVA will be used to examine the differences of change in serum biomarkers at week 12 compared to baseline in the TEHE only, Acupressure only, TEHEplus, TEHE +MBI and control (usual care) groups (***Aim 4***).

Sample size justification

Sufficient information from prior studies is not available for us to conduct a sample size calculation for the proposed multilevel analyses. The purpose of this pilot project is to explore the feasibility of the program and the relationships between the trajectories of the outcome measures, and not to achieve high power. The proposed N of 110 (22 participants/group) will likely result in low (below 0.60) statistical power. Results obtained will inform future power analyses for full-scale studies.

Early stopping criterion for safety/futility/efficacy as needed.

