activity and fatigue; (2) explore the effect of the combined TEHE program with Acupressure and MBI on fatigue and physical activity; and (3) determine the effectiveness of the TEHE alone, TEHEplus, and MBI+TEHE programs on serum biomarkers (Heat Shock Protein 90 and Brain-Derived Neurotrophic Factor) compare to control (usual care) group. A Safety Monitoring Committee (SMC) will be formed, consisting of Johns Hopkins University clinician faculty members who are independent of this proposed feasibility study. The SMC will be responsible for overall monitoring of the safety of participants in this proposed study and overseeing the PI, Co-Is, and research assistant.

The PI will be responsible for managing all data, securing privacy and confidentiality, minimizing and identifying risks, monitoring and reporting adverse events or any safety issues, and complying with timely reporting requirements to all applicable regulatory bodies for any adverse events or unexpected problems. Monthly reports will be completed by the PI detailing participant demographics, recruitment status, treatment retention rates, protocol compliance, data gathered and accuracy, and quality assurance or regulatory issues that transpired, and summary of any adverse events. The research team (PI, Co-Is, and research assistant) will meet weekly via face to face or conference calling to discuss data and safety monitoring.

The SMC will meet annually (or more frequently if needed) and review the annual reports completed by the PI; review study safety, integrity, and progress including any adverse events; provide advice about continuing, changing, or terminating the study when necessary; require more frequent reporting as needed; audit the study for compliance and verify the authenticity of data, and assess that the research team is complying with informed consenting and other required regulations. These annual meetings will be conducted face-to-face or through conference calls.

References

1. National Cancer Institute. SEER Stat Fact Sheets: Prostate Cancer. 2007-2011. <http://seer.cancer.gov/statfacts/html/prost.html>; 2014.

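### Primary Aim 2 is a comparison with usual care, but the analysis plan ties the programme effect to an uncontrolled paired t-test and does not rank it against the between-arm test

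*Combined protocol and SAP*

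**What the plan says.** Section 2 (Objectives) sets the second primary aim as "to determine the effect of the TEHE plus program on fatigue, physical activity and serum biomarkers", with usual care as comparator. Section 7, under Primary and secondary objectives, restates it as "the effect of the TEHE program and TEHE plus on fatigue, physical activity and serum biomarkers", again against usual care.

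The Section 7 analysis plan opens its Aim 2 text with "To examine the effect of the TEHE program on fatigue, physical activity and serum biomarkers" and then says that "the paired t-test will be used to analyze the effect of the program on fatigue, PA and biomarkers at the end of the program", compared with baseline. The following sentence begins "The student t-test will be used to compare the variables among participants in the TEHE program" and goes on to list Acupressure only, TEHEplus and TEHE+MBI, each set against usual care. It does not say whether that test uses week-12 values or change. No passage states which of the two tests answers Aim 2, which one is supportive, or what is concluded if they disagree.

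**The concern.** The trial is randomised with a usual-care arm so that change common to all arms can be removed. A paired test within an active arm credits all of that arm's change to the programme.

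The design leaves room for common change. Entry depends on the outcome domain: candidates are "screened by phone for the average fatigue level within the past 7 days at the level of 3 or more" out of 10 (Section 4), so regression to the mean in fatigue is possible. Monitoring is also shared by all participants, controls included: "Participants will be asked to wear the Fitbit on the non-dominant arm and respond to the mEMA daily for 12 weeks" (Section 4). The documents do not show that such change occurs, how large it is, or which way it goes.

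Two errors are possible. A significant pre-post change could be reported as the Aim 2 effect although usual care changed equally. Or usual care could worsen while an active arm holds steady, and the paired test would miss a real difference. The sample size section also says that the results will feed later power calculations, without saying whether the within-arm or the between-arm estimate will be used.

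**Working it through.** **1. Aim and tests side by side.**

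| Place | Arm(s) | Compared with |
|---|---|---|
| Section 2, Aim 2 | TEHE plus | usual care |
| Section 7, objectives, Aim 2 | TEHE, TEHE plus | usual care |
| Section 7, analysis plan, Aim 2 lead-in | TEHE | none named |
| Same, paired t-test | not named | own baseline |
| Same, Student t-test | TEHE, Acupressure only, TEHEplus, TEHE+MBI | usual care |
| Section 12, biomarkers only: "determine the effectiveness of the TEHE alone, TEHEplus, and MBI+TEHE programs on serum biomarkers" | TEHE, TEHEplus, MBI+TEHE | usual care |

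**2. What each test estimates.** Let mean change be *s* under usual care and *s* + δ in an active arm. Aim 2 asks about δ. The paired test estimates *s* + δ, and the between-arm test estimates δ. The two agree only if *s* = 0. If *s* = −δ, the paired test sees no change and misses δ. Running the paired test in controls as well gives *s*, but still no test of δ.

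**3. Inputs.** The Abstract gives N = 105, so 105/5 = 21 per arm. The sample size section gives 110, and 5 × 22 = 110 agrees with its 22 per group. The stated power (below 0.60) cannot be reproduced because no effect size, SD or alpha is given. With 22 per group and a two-sided 0.05 t-test, power reaches 0.60 at 0.68 SD, so the statement fits any smaller true difference. Everything below is illustration under assumptions: normal outcomes, two-sided 0.05, no dropout, no treatment effect.

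**4. Two unranked tests, no shared change.** Two tests at 5% each have a joint false-positive rate between 5% and 5% + 5% = 10%. In simulation with 21 per arm, an inert arm is significant on at least one test in 8.3–8.5% of trials if the between-arm test uses change, and 9.4–9.6% if it uses week-12 values.

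**5. Shared change of any cause.** Let the shared change be *d* SDs of the change score. The paired test has noncentrality *d*√n on n − 1 degrees of freedom. With n = 21:

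| *d* | *d*√21 | Paired test significant | Paired significant, t-test on change vs control not |
|---|---|---|---|
| 0.2 | 0.92 | 14.1% | 12.0% |
| 0.3 | 1.37 | 25.8% | 23.4% |
| 0.5 | 2.29 | 58.7% | 56.0% |

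The between-arm t-test on change stays near 5%. With n = 22 the paired figures are 14.6%, 26.9% and 60.9%.

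**6. Selection on the fatigue screen alone (fatigue outcomes only).** Assumed: 40, 55 or 75% of those screened pass; screen–baseline correlation 0.6, 0.7 or 0.8; screen–week-12 correlation 0.4, 0.5 or 0.6; baseline–week-12 correlation 0.5, 0.6 or 0.7. A combination is kept only if the screen–week-12 correlation is at least the product of the other two, so that the screen has no negative partial correlation with week 12 given baseline. There were 20,000 simulated trials per combination.

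| Baseline–week-12 correlation | Combinations kept | Paired rejection, n = 21 | Median | Maximum, n = 22 |
|---|---|---|---|---|
| 0.5 | 27 | 4.9–43.0% | 8.8% | 44.8% |
| 0.6 | 21 | 4.9–31.5% | 7.8% | 32.7% |
| 0.7 | 15 | 4.8–20.1% | 7.5% | 21.3% |

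At n = 21, 41 of the 63 combinations (27 + 21 + 15) are below 10% and two exceed 30%. The 43.0% is one corner: 40% pass, correlations 0.8, 0.4 and 0.5. There the mean screen value among those passing is φ(0.253)/0.40 = 0.386/0.40 = 0.966 SD, and the shift is (0.4 − 0.8) × 0.966 = −0.386 SD. The screen is a phone rating while the outcomes are FACT-F and PROMIS-F, so a lower screen–baseline correlation is plausible. Capping it at 0.7 lowers the maximum to 25.7%. Over the same combinations the between-arm error is 4.6–5.6% (change), 4.7–5.3% (week-12 values) and 4.5–5.4% (ANCOVA).

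**7. What baseline adjustment adds.** With equal variances and baseline–week-12 correlation *r*, the variance of the between-arm difference is proportional to 1 for week-12 values, 2(1 − *r*) for change and 1 − *r*² for ANCOVA. At *r* = 0.5 these are 1, 1 and 0.75. The gain is in precision; error control is the same.

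**The case against.** The strongest reply is that the correct test is already in the plan. The sentence after the paired t-test compares every active arm with usual care, and since both statements of Aim 2 name that comparator, a careful reader can match test to aim. Means and SDs are also planned per group and visit, which would expose equal change in usual care. The study is a self-declared low-power pilot, and no decision rule uses the paired p-value. All of this stands and limits the consequence. It does not supply the missing ranking, and the plan attaches the programme effect to the other test.

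Aim 4 adds an ANOVA of biomarker change across all five groups, controls included. That is a second controlled analysis, but only for biomarkers, and it ranks nothing within Aim 2.

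The regression-to-the-mean argument applies to fatigue only, because physical activity and the biomarkers are not selected on at entry. That is right, and step 6 is limited accordingly. It is also right that the magnitudes rest on assumed correlations, pass rates and alpha. They illustrate how a pre-post test behaves and do not measure what will happen in this trial.

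Finally, ANCOVA goes beyond what the defect requires, since a between-arm t-test controls error equally well. That is accepted: ANCOVA is a precision gain available from data already collected, and naming the planned t-test would be enough.

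**Conclusion.** The concern holds, with moderate consequence. As written, Aim 2 asks for a difference from usual care, while its analysis text describes the programme effect through a test with no control, next to an unranked controlled test. The arms in the primary contrast are also not settled. These points rest on the text alone and need no assumption.

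The size is illustrative. Having two unranked tests raises the chance of a spurious finding for an inert arm from 5% to about 8–10% even with no shared change. Selection on the fatigue screen alone gives a paired-test error with medians of about 8–9% and, in one extreme combination, 43%. Larger shared changes give 14–59% over 0.2 to 0.5 SD of the change score. A comparison with control stays near 5% throughout. This should be corrected before analysis, but it does not invalidate the trial.

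**What to change.** Replace the Aim 2 analysis text with wording such as:

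> Aim 2 is answered by the difference between [the arm or arms named in Aim 2] and usual care at week 12, adjusted for the baseline value (ANCOVA), with a 95% confidence interval. Change from baseline within a group is supportive and is not a test of programme effect. Effect sizes for future power calculations will come from the between-group difference.

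Make Section 2, the Section 7 objectives and the Section 7 analysis plan name the same arm or arms as the primary contrast, and align Section 12. The minimum change is to name the already planned between-arm t-test as the Aim 2 analysis, state whether it uses change or week-12 values, and label the paired test supportive.

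The cost is wording only. Baseline values are already collected at study visit 1, so no new data or participants are needed. Within-arm p-values lose their status as evidence of effect.

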Demographic and disease information questionnaire	X													
FACT-F and PROMIS fatigue	X													X
PROMIS Adult profile	X													X
Cognitive function (MOCA and MASQ)	X													X
Physical activity (steps) and HR (from the wearable device)*	X	X	X	X	X	X	X	X	X	X	X	X	X	X
Muscle strength test	X													X
Short-form survey (SF-36)	X													X

Date: September 26, 2024

Principal Investigator: [name]

Application Number: IRB00154198

Connor-Davidson Resilience Scale	X									X
Coping self-efficacy scale	X									X
Pittsburg Fatigability Scale (PFS)	X									X
Physical performance	X									X
Heart rate variability	X									X
Blood sample for HSP90 and BDNF level	X									X
Open-ended questions about the feasibility of the program										X
MRS for the central and peripheral markers (sub-study)	X									

Randomization:

After the baseline data collection and blood draw, the participants will be stratified by type of cancer (breast cancer vs. prostate cancer), age, and treatment (completed treatment vs. receiving immunotherapy). Participants will be randomly assigned to the control and intervention (TEHE only, TEHE plus, Acupressure only, TEHE +MBI groups) groups. The participants' random group assignment will be determined using the Excel program.

Participants in the experimental groups will receive either a) 45-60 min online exercise training/consultation session only, b) an online exercise training session and online and written APA instruction (TEHE +Acupressure group), c) online and written APA instruction only or d) exercise training instructions and mindfulness relaxation instructions (TEHE + MBI groups). After the exercise training session, participants will select their preferred exercise type and their preferred follow-up methods, duration of exercise, exercise schedule, and exercise frequency for the next 12 weeks. Participants will receive weekly recommendation for physical activity goals, recommended acupressure points (for TEHEplus and Acupressure only groups) and recommended mindfulness techques (for TEHE + MBI group). Participants in the control group will continue with their daily usual physical activity.

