The purpose of this pilot study is to examine the feasibility of the interventions. Therefore, participants may be asked to stop their participation early if there are serious complications include metastasis of the disease is found, serious injuries (broken bone, severe muscle injury) that prohibit the participants to exercise, severe infection during the 12 weeks intervention (e.g., fever, redness, swelling, etc.).

Inclusion and exclusion criterion: please see section 5.

Intervention/Independent Variables.

Technology-Enhanced Home Exercise (TEHE) Program: An online individual exercise session will be offered at the first study visit. Participants will be complete an exercise training program (45-60 min) to reach a moderate intensity using the heart rate monitor and exertion level.

The online exercise training/consultation program will include

- Goal setting/discussion of the progress (25 min): Participants will spend 25 min to discuss the physical activity barriers and set up a goal for the program.
- Exercise safety and body alignment (10 min): Participants will learning about posturing and body alignment to maintain their safety during exercise and monitoring the heart rate using the wearable device.
- Review physical activity and symptoms (15 min)
- At the end of the program, participants will select follow up methods (phone or video call), reminder message scheduled time and frequency.

At home: Participants will receive a weekly recommendation through a smartphone application and be instructed to follow their physical activity/step goals. Participants will receive a summary report of their weekly physical activity and symptoms (Fitbit and mobile phone application data).

The PI ([name]) will monitor the intervention session to ensure intervention fidelity. Adherence to the intervention will be assessed by data collected from the activity tracker on minutes of moderate-intensity or greater activity. At the end of the 12 weeks, participants will answer open-ended questions about their satisfaction with the program.

The Acupressure program: Participants in this group will receive online or in person auricular point acupressure (APA) and body pressure points training at the first study visit. An online educational video and written material developed by interventionists and PI, will

Figure 3. Ear Points for Fatigue

Date: September 26, 2024

Principal Investigator: [name]

Application Number: IRB00154198

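### Between-arm tests for Aims 2 to 4 use neither baseline nor stratification factors as covariates, and Aim 2 does not say whether week-12 values or changes are compared; the cost is precision, not bias

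*Combined protocol and SAP*

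**What the plan says.** Section 7 (Study Statistics, Analysis plan) is the only place where between-arm tests are defined.

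- **Aim 2 (primary).** A paired t-test compares week 12 with baseline. Between arms, "The student t-test will be used to compare the variables among participants in the TEHE program, Acupressure only, TEHEplus, and TEHE +MBI" against usual care. The scale of the variables is not given.
- **Aim 3.** Under the secondary aims: "The change of fatigue and physical activity level in week 12 compared to baseline will be calculated". ANOVA follows, so by context it is applied to the change.
- **Aim 4.** "ANOVA will be used to examine the differences of change in serum biomarkers at week 12 compared to baseline" across the five groups.

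None of these sentences names a covariate. The sample size paragraph refers to multilevel analyses, but no such model is described anywhere.

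Section 4 (Randomization) says "After the baseline data collection and blood draw, the participants will be stratified by type of cancer (breast cancer vs. prostate cancer), age" and treatment status. For the questionnaires, then, a baseline before assignment is planned and three prognostic factors are recorded.

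For two outcomes the timing of baseline is less tidy:

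- **Blood.** Section 4 says "Peripheral blood will be drawn at week 1 and week 12 for participants who can complete the study visit in person". The Methods paragraph of the abstract, the Randomization text and both copies of Table 1 indicate a first draw before the program.
- **Steps.** "Participants will be asked to wear the Fitbit on the non-dominant arm and respond to the mEMA daily for 12 weeks" is the only wear instruction. The Table 1 in section 4 has a Baseline column separate from the numbered weeks; the Table 1 in section 7 does not. Neither gives the length of a baseline window or its order relative to assignment. On training, section 7 says "An online individual exercise session will be offered at the first study visit".

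**The concern.** The trial collects a baseline for its outcomes and stratifies on three factors, then uses none of them as covariates in the comparisons. Change scores do subtract baseline, but with a fixed coefficient of 1. Week-12 values ignore it. With about 22 per arm and power that the plan itself puts below 0.60, this gives up precision that data already scheduled could supply.

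The gap in Aim 2 is a separate matter. Change is introduced only under the secondary aims, so the primary t-test could be run on either scale. Power on the two scales can differ widely depending on the correlation between baseline and week 12. Leaving the scale open allows the choice to be made once the data are known. It also weakens the results as input to later power analyses, which is the use the sample size paragraph gives for them.

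**Working it through.** **The plan's own figure.** 5 x 22 = 110, which agrees with the sample size paragraph. (The abstract gives 105, or 21 per arm if equal.) The stated power, below 0.60, cannot be reproduced because no alpha, effect size or SD is given. For a two-sided 0.05 t-test with 22 per arm it corresponds to a standardised difference d below 0.683.

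**Inputs.** From the documents: n = 22 per arm. Assumed, because the documents do not give them: d = 0.5, two-sided 0.05, equal SDs (set to 1), no dropout, and a baseline to week-12 correlation r from 0.3 to 0.8. The only related figure is the FACT-F test-retest value of 0.90, which is not a 12-week correlation under treatment.

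**Variance of the difference between two arms.**

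- Week-12 values: 2/n
- Change: (2/n) x 2(1 - r)
- ANCOVA: (2/n) x (1 - r²) x [1 + 1/(2n - 4)]. The last factor is the cost of estimating the slope; at n = 22 it is 1 + 1/40 = 1.025.

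**Example, r = 0.5.** The standard error is √(2/22) = 0.3015 for week-12 values and for change, since 2(1 - 0.5) = 1. For ANCOVA it is 0.3015 x √(0.75 x 1.025) = 0.2644. The 95% half-widths are 2.018 x 0.3015 = 0.608 SD (42 df) and 2.020 x 0.2644 = 0.534 SD (41 df). The noncentralities are 0.5/0.3015 = 1.658 and 0.5/0.2644 = 1.891.

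**Power from the noncentral t, 22 per arm, d = 0.5.** The last two columns give the ANCOVA variance reduction, slope cost included.

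| r | Week-12 value | Change | Two-arm ANCOVA | vs week-12 | vs change |
|---|---|---|---|---|---|
| 0.3 | 0.367 | 0.278 | 0.389 | 7% | 33% |
| 0.5 | 0.367 | 0.367 | 0.455 | 23% | 23% |
| 0.7 | 0.367 | 0.552 | 0.610 | 48% | 13% |
| 0.8 | 0.367 | 0.726 | 0.760 | 63% | 8% |

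With 21 per arm, ANCOVA power is 0.373, 0.437, 0.589 and 0.739.

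**Where ANCOVA wins.** Against week-12 values: (1 - r²) x 1.025 < 1, so r > √(1 - 1/1.025) = 0.156. Against change: (1 + r) x 1.025 < 2, so r < 0.951. It has the smaller variance of all three for r between about 0.16 and 0.95.

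**Five-arm model.** Simulation with 20,000 runs per setting covered baseline, age, treatment status and a three-level cancer type, with strata that explain nothing. Power was 0.384, 0.451, 0.608 and 0.763 at N = 110 for the same four r values, and 0.374, 0.439, 0.597 and 0.742 at N = 105. The extra covariates cost almost nothing even when they do not help.

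**The case against.** The strongest reply is that nothing here is invalid. Arms are randomised, so an unadjusted comparison of week-12 values or of changes is unbiased when baseline precedes assignment and follow-up is complete. The study is a declared pilot that does not aim for high power. Aims 3 and 4 already use change, and at r of 0.7 to 0.8 ANCOVA adds only about 0.03 to 0.06 of power over change (0.610 - 0.552 = 0.058; 0.760 - 0.726 = 0.034). Both r and d are assumed. All of this stands. It limits the size of the point but does not answer it: Aim 2 does not commit even to change, and the better analysis is nearly free.

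A reader might go further in four ways that the documents do not support.

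- **That the planned tests are biased.** With a true baseline and complete follow-up they are not.
- **That week-1 steps, already affected by treatment, will serve as baseline.** Nothing says so, and one Table 1 schedules a separate Baseline column for steps. What is missing is the window's length and its order relative to assignment. The steps row also carries an asterisk whose note is not in the text available for this review.
- **That baseline blood is taken after assignment.** One mention of week 1 stands against the abstract, the Randomization text and both tables. It is most naturally a loose label for study visit 1.
- **That ANCOVA is better at every correlation.** That is a large-sample result; at this size the range is the one derived above.

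**Conclusion.** The concern holds as a loss of precision and an unspecified primary comparison. No between-arm test for Aims 2 to 4 uses the baseline value or the stratification factors as covariates, the multilevel analyses are never specified, and the Aim 2 quantity is left open. The paired t-test works within arms and supplies no between-arm adjustment.

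Under the stated assumptions the gain in power over week-12 values runs from 0.02 at r = 0.3 to 0.39 at r = 0.8. Over change it runs from 0.11 down to 0.03. The choice left open in Aim 2 alone moves power from 0.367 to anywhere between 0.278 and 0.726 over the same range of r. The gain from the strata cannot be quantified from the documents, and adjustment does not turn the pilot into a well-powered trial. The absence of covariates is plain from the text; the sizes depend on r, d, equal SDs and no dropout. This is a change the sponsor should make, not a defect that invalidates the analysis.

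**What to change.** In section 7, replace the between-arm t-tests and ANOVAs for Aims 2 to 4 with one linear model per outcome across all five arms: week-12 value on arm, pre-randomisation baseline value, age (continuous), treatment status and cancer type, coded as actually used at randomisation. Take the contrasts for each aim, with 95% CIs, from that model. Then:

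- **Baseline.** Use only values measured before assignment.
- **Biomarkers.** Only in-person participants give blood, so keep covariates sparse, with the baseline value first. Align the week 1 wording in section 4 with the abstract, the Randomization text and both tables.
- **Steps.** Reconcile the two versions of Table 1 and state the baseline window and its order relative to assignment. If there is no wear before assignment, analyse week-12 steps adjusted for the stratification factors only. Power under that fallback is 0.364 against 0.367 unadjusted, even if the strata explain nothing.
- **Multilevel analyses.** Specify them consistently with this model or delete the phrase.

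The cost is SAP wording and about 5 of 110 - 5 = 105 residual degrees of freedom: one each for baseline, age and treatment status, and two for a three-level cancer type. The third level is counted because section 5 admits other solid tumours under immunotherapy, while the Randomization text names only breast and prostate. No new data are needed.
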